## 3. Quality Performance Indicators

Multiple practice guidelines have been published for the management of AP (14–19). The recommendations in these guidelines are usually based on a systematic review of the relevant literature and the evidence on which is based on the available evidence, which is usually graded. Quality performance indicators will be drawn from these evidence-based recommendations for each of the nominated management domains that are relevant to the management of patients within the first 72 hours from admission to hospital. Any differences in the recommendations between the source guidelines will be resolved by discussion amongst the Scientific Advisory Group and consensus established for the QPIs.

The QPIs were developed for the following management domains: (Appendix D: Table 1 with guidelines)

**Table 1.** Quality Performance Indicators

	Domain	QPI	Ref*	Metrics
1	Diagnosis	All patients diagnosed within 12 hours of admission	IAP	RAC criteria for diagnosis: enzymes 3xUL, typical pain ± CT scan
2	Aetiology	All patients had tests for aetiology determined within 24 hours of admission	IAP	U/S for gallstones ETOH history with intake (units per week, timing of binge to pain) If both negative then lipids, IgG4, drugs
3	Severity (predicted)	All patients had prediction of severity on admission	IAP	N / Y, if yes method (drop-down of all options and other) Further drop-down bar will the give options for severity (mild, moderate, and severe)

4	Severity (actual)	All patients had actual severity determined at 48 hours	-	N / Y, if yes method (drop-down RAC, DBC and other) Further drop-down bar will the give options for severity (mild, moderate, and severe)
5	CT scan	Initial CT assessment performed after 72-96 hours if poor response to initial management or clinical deterioration, unless there is diagnostic uncertainty. Not required for severity prediction.	IAP	N / Y, if yes indication (drop-down with other)
6	Transfer	All patients with predicted or actual severe AP in the first 72 hours are discussed with specialist pancreas service.	Nice	N / Y Indication for transfer (drop-down)
7	Analgesia	All patients given narcotic analgesia within one hour of admission	-	Step-up or step-down approach? IV analgesia given on admission N / Y NSAIDS given to mild AP Analgesics prescribed

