8	Fluids	
 
All patients commenced on IV Hartmann's solution within one hour of admission to the emergency department by a clinician and at an initial rate of 5-10 ml /kg in response to hypovolemia until resuscitation goals reached.
 
Then a rate of 1-2 ml/kg/hour for patients not tolerating PO in the first 48 hours.
 
	IAP	IV fluids N / Y Time commenced from admission What initial fluid was given? Initial prescribed rate Initial received rate Average rate 2 nd 24 hours Average rate 3 rd 24 hours Fluid bolus given (# times and and timing) Volume / 24 hours over 72 hours?
9	Anticoagulation	All patients with predicted severe AP considered for or started on anticoagulation within 24 hours of admission	-	Anticoagulation N / Y Medication prescribed When started (hours from admission)
10	Antibiotics	Antibiotic prophylaxis not recommended for the prevention of infectious complications in AP	IAP	Antibiotic N / Y Antibiotic indication

11	Nutrition	
 
1. No patients made 'nil-by-mouth' and no food withheld unless there was a clear reason.
 
2. Offer EN to anyone with MSAP or SAP starting within 72 hrs.
 
3. PN avoided unless EN fails or is contraindicated
 
	NICE	Initial NBM N / Y From admission given trial of light diet. N / Y Initial NG or NJ? EN started within 72 hours if needed N / Y EN prescribed rate PN started if EN was not tolerated or contraindicated.
12	ERCP/ES	ERCP is indicated in patients with biliary pancreatitis and acute cholangitis within 48 hours of admission.	IAP	ERCP N / Y Indication: cholangitis or cholestasis When done? (hours)

\* Reference of guideline from which the QPI is primarily taken from

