## 5.5. Required data

Demographic details	
Age	Year of birth
Sex	Male/ Female/ Other
Ethnicity	European/ Pasifika/ Maori/ Asian/ Middle-Eastern/ Latin American/ African (MELAA)/ other ethnicity
Postcode	
Weight	kg
Height	cm
Smoking history	Current smoker /previous smoker /never smoker e-cigarette /cigarette
Admission details	
Date of first review by doctor/prescriber	Date (dd/mm/yyyy)  *From ED admission note
Time of first review by doctor/prescriber – as per admission note	24 hour clock time
Pancreatic enzymes at admission	Lipase/ Amylase/ Pancreatic amylase (tick one or more and give admission level and indicate what 3x upper limit is
Lipase/ amylase/ pancreatic amylase level	U/L
Epigastric pain confirmed on admission note	Yes/Non-epigastric abdominal pain/ No abdominal pain
Confirmation of AP diagnosis with imaging as per radiological report	MRI/ CT/ Abdominal USS
Charlson Comorbidity Index ( Appendix E )	Score out of 37
Aetiology	
Significant ETOH history investigated in first 72 hours	Yes - from medical history, Yes - ETOH blood test, No

Hypertriglyceridemia investigated in first 72 hours	Yes/No
Acute pancreatitis severity	
Predicted severity on admission as documented in clinical notes (72 hours)	Mild/ moderately severe/ severe
Method used to predict severity	Modified Glasgow/ Ransons'/ BISAP/ APACHE II/ SIRS/ CRP (>150)/ Other (please specify)/ Clinical judgement (no prediction tool)/ No prediction made.
Imaging	
CT assessment performed in the first 72 hours of presentation	Yes/ No
Indication for CT prior to 72 hours	Diagnostic uncertainty/ confirmation of severity based on clinical predictors of severe AP/ Failure to respond to conservative treatment or in the setting of clinical deterioration/ other (please specify)
Imaging of the gallbladder during admission	USS/ CT (gallstones seen on CT)/ MRI/ EUS/ prior imaging confirming gallstones/ previous cholecystectomy/ no imaging
Antibiotics	
Antibiotics administered in first 72 hours of presentation	Yes/ No
Indication for antibiotics	Cholangitis concomitant extrapancreatic infection/ prophylactic/ other – please state
Analgesia	
Simple analgesia (paracetamol/ NSAIDs) prescribed	Paracetamol/ NSAIDs/ Not charted
Simple analgesia frequency	regular/ PRN
Date simple analgesia first administered	Date (dd/mm/yyyy)

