Type of opioid prescribed (if any)	Codeine/ Morphine/ Fentanyl/ Tramadol/ Oxycodone/ Other (please specify)/ no opioids prescribed
Date opioid analgesia first administered	Date (dd/mm/yyyy)
Time opioid medication is administered to patient	24 hour clock
Route	PO/ IV
(If regular) daily dose	mg
(If PRN) total dose in first 72 hours	mg

(If yes) Date opioids first administered	Date (dd/mm/yyyy)
(If yes) Time opioid medication first administered as per drug chart?	24 hour clock
Further analgesic modalities	PCA/ ketamine/ local nerve blocks/ other (please specify)
Transfer to different hospital	
Patients with predicted severe disease discussed with specialised pancreas service ( Appendix B ) in first 72 hours from admission	Yes/ No/ not applicable
Patient transferred to a different hospital in the first 72 hours?	Yes/No
(If yes) Date of transfer	Yes/No
(If yes) Location transferred to	List of hospitals
(If yes) Reason for transfer to different hospital?	Severe disease/ requires ERCP/ requires interventional management of local complication/ other (free text)
ERCP	
Cholangitis in first 72 hours ( Appendix F )	Yes/ No
Cholestasis in first 72 hours (radiological + deranged LFTs)	Yes/ No
ERCP performed in the first 72 hours	Yes/ No
Fluid management*	
Baseline variables	
Bag 1	
Date of administration	Date (dd/mm/yyyy)
Time of administration	Time (24-hour)
Volume administered	Volume (ml)
How long does fluid run for?	Time (hours)
Type of fluid	0.9% Normal saline/ Hartmann's/ plasmalyte/ colloid/ 0.45 saline + dextrose/ 0.18 saline + dextrose/ other (please specify)
Further administration of intravenous fluid (IVF) in the first 3 days of admission? ( Appendix B )	Yes/no
Bag 2	
Date of administration	Date (dd/mm/yyyy)
Time of administration	Time (24-hour)

Volume administered	Volume (ml)
Time fluid is administered	Time (hours)
Type of fluid	0.9% Normal saline/ Hartmann's/ plasmalyte/ colloid/ other (please specify)
Further administration of intravenous fluid (IVF) in the first 2 days of admission?	Yes/no
Documented fluid review after 12 hours ( $\pm$ 4 hours)	Yes/no
Documented fluid review after 24 hours ( $\pm$ 4 hours)	Yes/no
Documented fluid review after 48 hours ( $\pm$ 4 hours)	Yes/no
Documented fluid review after 72 hours ( $\pm$ 4 hours)	Yes/no
Early Nutritional support	
On admission patient kept nil by mouth (NBM)	Yes/no

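### Section 5.5 lists neither the ERCP time nor the 48-hour actual severity that Table 1 requires, so QPI 12's time limit cannot be applied and QPI 4 cannot be scored

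*Protocol*

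**What the plan says.** Table 1 in Section 3 of the protocol sets out twelve management domains, each with an indicator and the metrics needed to judge it.

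- **Row 12 (ERCP).** The indicator is that "ERCP is indicated in patients with biliary pancreatitis and acute cholangitis within 48 hours of admission". Its metrics are whether ERCP was done, the indication, and the timing, given as "When done? (hours".
- **Row 4 (actual severity).** The indicator is "All patients had actual severity determined at 48 hours". Its metrics begin "N / Y, if yes method (drop-down RAC, DBC and other" and go on to a grade of mild, moderate or severe.
- **Row 11, second item (QPI 11.2).** Enteral nutrition is to be offered to patients with moderately severe or severe disease (MSAP or SAP), starting within 72 hours.

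Section 5.5 then lists the required data. Its ERCP block has three Yes/No items: "Cholangitis in first 72 hours", cholestasis over the same period, and "ERCP performed in the first 72 hours". Its severity block has two items: the grade, described as "Predicted severity on admission as" documented "in clinical notes (72 hours", and the method used for that prediction. Local complications and organ failure or support are recorded over the 30-day follow-up.

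The sole primary outcome (Section 4.1) is the proportion of patients managed in compliance with the indicators overall. Compliance by domain between hospitals is a secondary outcome (Section 4.2).

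**The concern.** A compliance indicator with a time limit can be scored only if the time is recorded, and an indicator about an assessment can be scored only if the form asks whether the assessment was made. Table 1 recognises both needs, but Section 5.5 does not carry them through.

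If the data collected are exactly those in Section 5.5, an ERCP performed after the 48-hour limit but before 72 hours counts as compliant. Row 4 applies to every patient, so its absence leaves a gap in each patient's overall compliance. An analysis plan cannot repair either fault, because no rule can recover a time or grade that was not recorded.

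QPI 11.2 has a milder form of the same problem: its action has a 72-hour window, but the severity that triggers the action cannot be dated.

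**Working it through.** No sample-size or power arithmetic is involved. The check compares rows 4, 11 and 12 of Table 1 with the items in Section 5.5, then looks for any other field, or any appendix definition, that could supply what is missing.

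| Table 1 requirement | Section 5.5 item | Result |
|---|---|---|
| Row 12: ERCP done | Yes/No over 72 hours | present |
| Row 12: indication | cholangitis and cholestasis, Yes/No over 72 hours | present in substance |
| Row 12: hour of ERCP | none | missing |
| Row 4: severity determined at 48 hours | none | missing |
| Row 4: method | method of prediction only | missing |
| Row 4: grade | predicted grade only | missing |
| Row 11: enteral nutrition within 72 hours | Yes/No over 72 hours | present, window matches |
| Row 11: MSAP or SAP | no grade; complications and organ failure or support to day 30 | derivable, not datable |

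Section 5.5 therefore carries 2 of 3 metrics for row 12 and 0 of 3 for row 4.

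**QPI 12.** No other field gives an ERCP time. The dated interventions concern infected collections, and the transfer block gives only the transfer date, destination and reason. A patient recorded as having no ERCP by 72 hours can be classified; a patient recorded as having one cannot be placed before or after 48 hours. Let n be the eligible patients, y those with ERCP by 72 hours, and u those among the y whose ERCP came after 48 hours. Compliance with the stated limit is (y - u)/n. Section 5.5 yields only y/n, which is too high by u/n, and u could be anything from 0 to y.

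**QPI 4.** The indicator asks whether severity was determined at 48 hours. A grade reconstructed later from complications and organ support would not show that anyone made the assessment at that time, or by which classification. The indicator therefore cannot be scored from Section 5.5. At most 12 - 1 = 11 of the twelve domains could contribute to overall compliance as Table 1 defines it.

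**QPI 11.2.** Section 5.5 records necrosis, necrotic and fluid collections, and portal or splenic vein thrombosis. It also records renal failure (including more than 48 hours), high-flow oxygen, non-invasive and mechanical ventilation, and inotropes, with durations for organ support. With Appendix A (i), these largely give MSAP or SAP at any time to day 30. None has an onset date; among the local complications, only interventions are dated. A patient who first meets the definition on day 10 therefore looks the same as one who met it on day 2. If the day-10 patient had no enteral nutrition by 72 hours, scoring on day-30 severity would record a failure although no trigger existed by the deadline.

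**The case against.** The strongest reply is that harm is not shown. Table 1 words its metrics as form items with drop-down lists, so the intention to collect them is on record. The REDCap form is a separate item in the Study Timeline and is not available here; it may hold every missing field. That stands, and it limits the point to the fields as listed. It does not remove the contradiction, because Section 5.5 is presented as the required data and differs from Table 1 on what is required. Retrieval is also possible: Section 5.3 keeps a key linking REDCap numbers to hospital identifiers.

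Three stronger readings are tempting, and the protocol does not support them.

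- A reader might infer that the group eligible under QPI 11.2 cannot be identified at all. It largely can, up to day 30. The indicator attaches its 72 hours to the start of nutrition, and the row 11 metric also refers to need. Only the presence of severity by 72 hours is out of reach.
- A reader might treat the missing onset time for cholangitis as a third contradiction. Table 1 does not list it as a metric. Without it, cholangitis arising after 48 hours cannot be separated from earlier cholangitis, but how often that happens is not stated. The 48 hours in row 12 can also be read as attached to either the ERCP or the cholangitis. Recording the onset is a worthwhile option, not a correction of a mismatch.
- A reader might take these gaps to be the only ones. They are not a full reconciliation: IgG4 testing and weekly alcohol units in row 2, for example, also have no item in Section 5.5.

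**Conclusion.** The point holds as a contradiction inside the protocol that reaches the primary outcome. Section 5.5 omits the ERCP time and all of the 48-hour actual-severity determination. On the listed fields, QPI 12's limit cannot be enforced between 48 and 72 hours, and QPI 4 cannot be scored. The dating of severity for QPI 11.2 is secondary, because it depends on which field is used to define eligibility, and the protocol does not say.

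The size that the text fixes is one of three row 12 metrics and three of three row 4 metrics missing. The effect on compliance cannot be quantified: the protocol gives no timing of ERCP or of MSAP or SAP onset, and no count of patients with biliary pancreatitis and cholangitis. The errors also differ in direction. A late ERCP counted as timely raises compliance; a late-onset severe case counted as a nutrition failure lowers it. The net bias has no known sign.

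The conclusion assumes that the data collected follow Section 5.5. If the REDCap form already holds the missing items, only the protocol list needs correcting. The change should be made, since it is cheap and later analysis cannot substitute for it.

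**What to change.** 1. In Section 5.5, add the date and time of ERCP.
2. In Section 5.5, add the row 4 items: actual severity determined at 48 hours (Yes/No), method, and grade.
3. Add either an actual-severity grade at 72 hours or onset dates for organ failure and local complications. The 48-hour grade alone is not enough for QPI 11.2, because disease can become moderately severe between 48 and 72 hours.
4. In row 11, state that eligibility for QPI 11.2 uses severity present by 72 hours.
5. Optionally, record the date and time when cholangitis was first documented, and state in row 12 that the 48 hours limits the ERCP.

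With the 72-hour grade chosen in item 3, the cost is 1 + 3 + 1 = 5 form entries and one sentence; onset dates would need more entries. The optional item adds one entry and one sentence. Section 5.5 already records dates and clock times for opioids and fluids. Section 5.3 has a collection point at 48 hours that suits the row 4 items, and Section 5.6 follows patients through 72 hours.

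If collection has finished, retrieve these items from the notes through the REDCap key where approvals allow, at the cost of a second chart review. Otherwise, report QPI 4, 11.2 and 12 with the limitation stated.

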## 4. Outcomes

### 4.1. Primary outcomes

- Proportion of patients that were managed in compliance with quality performance indicators overall

### 4.2. Secondary outcomes

- Variation in compliance with QPIs between hospitals for each of the management domains
- Requirement for mechanical ventilation (invasive and non-invasive)
- Requirement for renal replacement therapy
- Requirement for inotropic or vasopressor support
- Intervention for a complication of AP
- Alive and discharged at 30-days

[figure not shown]
## 5. Methods

### 5.1 Study Setting

PANORAMA welcomes the participation of any publicly funded secondary or tertiary hospital in AoNZ under the Te Whatu Ora Health NZ directorate. All centres intending to take part in the study must register in accordance with local regulations and proof of registration must be provided to ACTT before initiating the data collection process.

### 5.2. Study Design

This study will use the trainee-led collaborative research model successfully used in NZ and internationally. Each hospital will have a ‘mini team’ of collaborators which will include a supervising consultant, a hospital lead and data collectors (explained in Figure 1 below). These collaborators will include medical students, junior doctors, trainees, registrars, and supervising consultants (Figure 1). It is compulsory to have a consultant supervisor in each mini team who is able to provide guidance and advice around how the study may be registered at a hospital and the approvals that will be required.

**Figure 1.** Mini-team structure and responsibilities

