## Study Timeline

Dates	Description
10 February 2024	
 
● Preliminary protocol drafted
 
● Quality performance indicators finalised
 

March 21 2024	
 
● HDEC submission (expedited pathway) in
 
● Tupu grant application in
 

March 27 2024	
 
● Data collection form finalised/ redcap form created
 

April (first week) 2024	
 
● Second general meeting of investigators and protocol finalised
 
● Slide made for NZAGS conference and presented
 
● REDCap users generated and sent to investigators
 

April - June 2024	Centres recruited and locality ethics applications in 
 
● Prepare for data collection
 

01 July 2024	Data upload window opens
30 September 2024	Data upload window ends - REDCap locked for new entries
31 October 2024	30-day follow up from day of admission
November/December 2024-January 2025	Data analysis and manuscript writing

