### 5.3. Data Collection

An investigator at each contributing hospital will be appointed to be responsible for data collection of all appropriate patients. Patients for AP may be admitted under multiple teams, it is the hospital lead's responsibility to capture all patients with AP that occur during the study inclusion period.

Data will be collected and stored using the web application REDCap. This web application is encrypted with HIPAA-Security, compliant with guidelines in the United States, and is widely used by academic institutions.

REDCap is a secure, web-based software platform designed to support data capture for research studies. It provides: 1) an intuitive interface for validated data capture; 2) audit trails for tracking data manipulation and export procedures; 3) automated export procedures for seamless data downloads to common statistical packages; and 4) procedures for data integration and interoperability with external sources.

Clinical data at each participating hospital will only be accessed by medical students and resident medical officers who already have access to the clinical data being collected. Individuals working at other centres, and those without access to patient clinical data, will not be involved in data collection. Locality approval will be sought and obtained at all centres prior to study commencement. An excel spreadsheet will be kept alongside the REDCap database at each hospital. This will be stored on a password protected hospital computer at each hospital. A unique RedCap number will be created for each patient. This number will allow re-identification of patients by the local hospital lead if required. After data has been uploaded into REDCap the local hospital copy of the data will be destroyed to protect patient privacy. An excel spreadsheet containing the REDCap key and the relevant patients NHI will be kept. This excel spreadsheet will allow future patient re-identification if required. During REDCap data upload there will be no data fields where identifiable data can be uploaded; for example, names or NHI's. Local excel files will be stored at each hospital for 10 years and destroyed following this. The central de-identified data set will be stored for 10 years using REDCap electronic data capture tools.

If further studies using this data set are to be performed a subsequent ethics application will be required before its use.

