All hospital leads will also be required to complete a hospital-survey which assess hospital-related variables (*Appendix C*).

Data collection will occur at two timepoints. The first time point will be within or at 48 hours of admission to hospital and secondly at 30-days follow-up following admission to the emergency department .

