## 5.6. Follow-up

All patients will be followed for the initial 72 hours following admission into ED by a clinician and then again chart reviewed at 30 days from initial admission.

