## 6. Ethical and regulatory considerations

### 6.1 Ethical considerations

This study will take the form of a prospective cohort study. There will be no change to the management of patients, no advice or guidelines given to the data collectors/clinical team. The aim will be to collect information on the routine practice of different hospitals around AoNZ. There is no foreseen impact on standard patient care and therefore no risk to patients involved in this study. There will be no contact with patients and follow-up data will be collected from routine clinical notes; No phone calls will be made.

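### Collectors may be treating the patients they audit and, at 48 hours, may open the form while some indicators can still be met, so the study may raise the adherence it measures

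*Protocol*

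**What the plan says.** **Who collects.** Section 5.2 describes a mini-team at each hospital: "These collaborators will include medical students, junior doctors, trainees, registrars, and supervising consultants". Section 5.3 states that clinical data "will only be accessed by medical students and resident medical officers who already have access to the clinical data being collected" and keeps staff of other centres out of data collection. Section 9 allows up to 8 data collectors per hospital. Neither the section 5.5 data fields nor the hospital survey in Appendix C asks whether the collector was also treating the patient.

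**When they collect.** Section 5.3: "The first time point will be within or at 48 hours of admission to hospital". Section 5.6: "All patients will be followed for the initial 72 hours following admission into ED by a clinician". Many section 5.5 fields refer to the first 72 hours.

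**What is to be measured.** Section 6.1: "The aim will be to collect information on the routine practice of different hospitals around AoNZ". The same section promises no change to management and "no advice or guidelines given to the data collectors/clinical team". The primary outcome (section 4.1) is the proportion of patients managed in compliance with the quality performance indicators (QPIs) overall. Variation between hospitals is a secondary outcome (section 4.2) and is shown in funnel plots (section 8).

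**The concern.** The study wants to describe routine care, but the people who fill in the form may be the people giving that care. If the form is opened while an indicator can still be satisfied, a blank item can act as a reminder. A collector who finds no documented severity prediction, or no discussion with a specialist pancreas service, may be in a position to supply it. Prompting of this kind would most likely raise measured adherence.

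Two results are exposed. One is the primary outcome. The other is the comparison between hospitals, because the overlap between collectors and treating teams may differ by site, and a difference in prompting would then look like a difference in care.

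**Working it through.** The protocol gives no sample size, expected adherence or estimate of overlap, so there is no planned figure to reproduce. The check has two parts.

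**1. Which indicators can still change when the form is opened?** Windows are taken from Table 1 (section 3) and from the section 5.5 fields.

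| Indicator | Table 1 | Section 5.5 field | Open just after 48 h? | Open after 72 h? |
|---|---|---|---|---|
| Specialist discussion (QPI 6) | 72 h | 72 h | Yes | No |
| Enteral nutrition (QPI 11, part 2) | 72 h | 72 h | Yes | No |
| Predicted severity (QPI 3) | On admission | Documented within 72 h | Only as the form records it | No |
| Antibiotics (QPI 10) | None stated | 72 h | As the form records it | No |
| ERCP (QPI 12) | 48 h | 72 h | Only as the form records it | No |
| Alcohol and triglyceride work-up (QPI 2) | 24 h | 72 h | Only as the form records it | No |

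Diagnosis (12 h), anticoagulation (24 h), analgesia (1 h) and the start of fluids (1 h) have closed by 24 h under Table 1. A form opened later than that cannot change them in the same patient. After 72 h two items remain: the CT indicator, which Table 1 places at 72-96 h although the form records only CT in the first 72 h, and gallbladder imaging, which the form records for the whole admission. Moving collection past 72 h therefore removes nearly all same-patient prompting.

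**2. How large could the effect be?** For one indicator that is still open:

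bias = f × c × (1 − p)

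Here p is true adherence, f is the share of patients whose collector is also treating them, and c is the share of those patients' misses that the form turns into compliance. All three are assumptions. At p = 50%, in percentage points:

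| f | c = 0 | c = 10% | c = 30% |
|---|---|---|---|
| 10% | 0 | 0.5 | 1.5 |
| 25% | 0 | 1.25 | 3.75 |
| 50% | 0 | 2.5 | 7.5 |

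At the top corner (f = 50%, c = 30%), p = 30% gives 0.5 × 0.3 × 0.7 = 10.5 points and p = 90% gives 0.5 × 0.3 × 0.1 = 1.5 points.

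*Between hospitals.* With p = 50% and c = 30%, a site with f = 50% and a site with f = 10% would differ by 7.5 − 1.5 = 6 points with identical underlying care.

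*Against sampling error.* The 95% half-width at p = 50% is 1.96 × √(0.25/n). For assumed totals of n = 400 and 600 it is 4.9 and 4.0 points. Enteral nutrition (QPI 11, part 2) applies only to moderately severe or severe disease, which section 1 puts at 20%. That leaves n = 80 to 120 and half-widths of 11.0 to 8.9 points. So the upper end of the bias (7.5) exceeds the sampling error for an indicator that applies to everyone, such as predicted severity, but not for enteral nutrition.

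**The case against.** **The timing conflict.** The case rests on the 48-hour statement in section 5.3. Section 5.6 follows patients for 72 hours, and some section 5.5 fields, such as the 72-hour fluid review and oral intake by 72 hours, cannot be completed at 48 hours. In practice the form may be finished after the windows close. This stands in part. The protocol contradicts itself here, and the conflict should be resolved first. It does not remove the point, because section 5.3 is the only statement of when data are collected early, and a form finished at 72 hours may have been opened sooner.

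**Section 6.1.** A reader might infer that the protocol breaks its own promise by giving collectors guideline-derived targets. The documents do not support that. The sentence most naturally means that the study issues no management advice. Nothing says that Table 1 is handed to collectors, and the QPIs come from published guidelines in any case. What remains is loose wording.

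**Actual severity at 48 hours (QPI 4).** This might look like the clearest open indicator. Section 5.5 has no field asking whether actual severity was determined at 48 hours, so the listed form cannot prompt it through a blank item.

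**Whether overlap can be traced.** A reader might conclude that it could never be checked. Individual logins (section 6.3), audit trails and the locally held patient key (section 5.3) might allow some reconstruction. The protocol plans none, and these records do not by themselves show who was treating the patient.

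**Who the collectors are.** Medical students are among them, and they are less likely to be directing care. This lowers the plausible overlap but does not make it nil.

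**Conclusion.** The point holds as a risk. Nothing in the protocol separates collectors from treating clinicians or records when they coincide. As section 5.3 is written, the form may be opened while specialist discussion, enteral nutrition and predicted severity (by the form's own window) can still be met. This may raise measured adherence above routine adherence, and may do so unequally across hospitals.

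The size is unknown. Under the assumptions above it runs from 0 to 7.5 points on a single open indicator at 50% true adherence, and up to 10.5 points over the wider range. Every input is assumed and zero is possible. The effect on the overall primary outcome depends on how the indicators are combined and is not computed here. Specialist discussion and enteral nutrition concern only a minority of patients.

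A reader might go further and say that the study does prompt the care it measures and does overstate adherence. The documents show the opportunity, not the effect. This is a cheap improvement to the design and does not invalidate the study.

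**What to change.** 1. **Timing (sections 5.3, 5.5, 5.6).** Reconcile the 48-hour collection point with the 72-hour follow-up and fields, so that the early form is completed only after the 72-hour windows close. Where a Table 1 window and its field differ (predicted severity, ERCP, aetiology), those entries must also be reconciled.
2. **Collector (sections 5.2, 5.3).** Where possible, a patient's form is completed by a mini-team member who is not treating that patient. Add one Yes/No field: 'collector was in the treating team'.
3. **Analysis (section 8).** Report QPI adherence by that field and by study month as a sensitivity analysis. The monthly table addresses learning across patients over the three months, which later collection does not prevent. Neither comparison is randomised, so they can expose reactivity but cannot measure it cleanly.
4. **Wording (section 6.1).** Say that no management advice is given, and state reactivity as a limitation.

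**Cost.** One form field, one instruction, one table and some allocation effort. With up to 8 collectors per hospital no extra staff should be needed, though small sites may only be able to record the overlap. There is one knock-on effect. The Study Timeline locks REDCap for new entries on 30 September 2024, and a patient admitted on 28 September reaches 72 hours on 1 October. Either the lock moves by at least three days, or the record is created before the lock and the early form is filled in afterwards.
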